Aim 2: Determine the feasibility of the efficacy study design. Feasibility will be assessed by examining the following outcomes related to recruitment, retention, and provider adherence: (1) number of participants approached for the study who are eligible and of those, the number who enroll in the study (i.e., agree to participate). Feasibility is defined as $\geq 50\%$ eligible and of these $\geq 30\%$ willing to participate in the proposed time frame. (2) participant completion of ACT-MI will be measured by the percentage of participants who complete treatment and receive an adequate dose (complete a minimum of 70% of the intervention). (3) percentage of participants lost to follow up (LTFU). The percentage of participants who fail to complete one- month and three-month follow-up visits will be measured, with $\leq 30\%$ LTFU considered feasible, informing

the necessary sample size and treatment retention strategies for future studies. (4) treatment fidelity checklists will examine provider adherence to treatment, with $\leq 15\%$ of deviations to be considered acceptable fidelity.

Aim 3: Select measures and calculate the necessary sample size for a future efficacy study.

Evaluate candidate measures based on the following factors: (1) Amount and distribution of missing data, (2) means and standard deviations, and (3) correlations with a measure of self-reported clinically significant change. Estimates of variability in outcome measures will inform power analysis and target sample size for a future efficacy study.

With the onset of the COVID-19 pandemic, it has become clear that the feasibility of delivering interventions through telehealth may be critical to their utility and that research methods must also be feasible for use through telehealth. Two aims related to conducting ACT-MI using telehealth are being evaluated:

Aim 4: Evaluate the acceptability of the ACT-MI intervention delivered over telehealth. ACT-MI will be delivered over telehealth as needed due to the COVID-19 pandemic. Acceptability of in person and telehealth data will be analyzed separately.

Aim 5: Evaluate the feasibility of the efficacy study design with all assessment sessions delivered over telehealth. ACT-MI and all assessment sessions will be delivered over telehealth as needed due to the COVID-19 pandemic. Feasibility of in person and telehealth data will be analyzed separately.

II. Background and Significance:

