Brief Addiction Monitor-Revised (BAM-R)¹⁰⁰⁻¹⁰¹ is a 17-item self-report measure developed by researchers at the Philadelphia Veterans' Administration Medical Center to assess symptoms of Substance Use Disorder. The BAM-R can be scored using a three-factor structure (substance use severity, risk factors, and protective factors) and shows reliability and validity in Veteran samples (Duration: 5 minutes). **Adult Suicidal Ideation Questionnaire** (ASIQ)⁹² is a 25-item self-report measure of suicidal ideation that will be used to assess changes in suicidal ideation. Reliability and validity have been demonstrated in clinical and community samples⁹³ (Duration: 10 minutes). **The Expressions of Moral Injury Scale (E-MIS)**⁸⁷ is a 17-item self-report scale that is used to measure expressions of moral injury related to how experiencing morally injurious events may affect one's emotional well-being, relationships and quality of life. The E-MIS measures self-directed (e.g., "I am ashamed of myself because of things I did/saw during my military service") and other-directed (e.g., "I feel anger over being betrayed by someone who I had trusted while I was in the military") subtypes of moral injury. (Duration: 7 minutes). The **Global Ratings of Change Scale (GC)** is a 6-item scale developed for the proposed study to assess self-report change following the interventions (e.g., "my current ability to live consistently with my values is _____ than my ability to live consistently with my values before I enrolled in the study."). The GC uses a 15-point Likert-type rating scale ranging from -7, "a great deal worse," to +7, a great deal better. The GC follows guidelines for an anchor-based approach to determining the minimally clinically important difference.³⁴ (Duration: 3 minutes; Administration: Post-Treatment, One-month follow-up, Three-months follow-up).

B. Description of Population to be Enrolled:

All data will be collected from eligible and willing Veterans that meet the following eligibility criteria:

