Inclusion Criteria: 1) Eligible for VHA care (information obtained from review of medical record), 2) Age 18-89 (information obtained from review of medical record), 3) Has been deployed to a warzone (information obtained from Veteran self-report/screening interview), 4) Has experienced a morally injurious event which continues to interfere with functioning (information obtained from Moral Injury Events Scale [MIES], Moral Injury Questionnaire-Military Version [MIQ-M], and self-report/screening interview), and 5) Willing to be randomized and participate in either of the two conditions (information obtained from Veteran self-report/screening interview). 6) When groups are only being offered through videoconferencing, participants will need a computer/smartphone capable of accessing the VA approved videoconferencing platform in a private setting.

Exclusion Criteria: 1) Inability to demonstrate understanding of the postcard consent (as evidenced by inability to respond correctly to postcard consent questions or medical record review), 2) Inability to complete study measures (e.g., due to significant acute intoxication/withdrawal symptoms, mania, psychosis, aggression, catatonia, cognitive impairment) (results of veteran self-report, screening, or discretion of interviewer), 3) Imminent suicide risk (medical record or UWRAP), 4) Membership in a vulnerable population (e.g., pregnant women) (medical record or self-report), 5) History of significant violence towards VA staff (medical record), 6) Participation in another psychotherapy research study, (medical record

or self-report), and 7) Current participation in an EBP for a condition related to moral injury (medical record or self-report).

C. Study Design and Research Methods

Design: We are proposing a two arm, randomized, controlled pilot study to assess the feasibility of a future randomized clinical trial (RCT) evaluating the efficacy of ACT-MI. Candidate measures for a future efficacy trial will be administered at baseline, post-treatment, and one- and three-month follow-ups. Measures of acceptability will be administered following treatment completion/discontinuation. Veterans who are eligible to receive treatment at the VA ECHCS and who are eligible and interested in participating in the study will be enrolled and randomized to: (1) Present Centered Therapy (PCT-MI) or (2) ACT-MI.

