Preliminary Screening. Preliminary screening will occur in person or by telephone. After detailed information about the study is shared, potential participants will be given the option to provide verbal consent and complete a verbal screening interview based on inclusion and exclusion criteria. Research personnel will also review the Veteran's medical records to further evaluate study eligibility. Following the screening, potential participants will be scheduled for their Baseline Assessment. Their appointment may also be confirmed via text message. ***Baseline Assessment Session and Randomization.*** Baseline assessment sessions will be conducted in person when possible. When necessary, baseline sessions will be conducted online using REDCap and telephone/videoconferencing. A waiver of consent and HIPAA are being requested to allow for a consent process with a postcard consent rather than a formal physical signed consent form. After demonstrating understanding of the postcard consent and indicating willingness to participate, participants will complete the safety measure (UWRAP) and then assessment measures (SCID-5 modules, C-SSRS, VLQ, PROMIS, OQ-45, PHLMS, AAQ-II, AAQ-II past week MEAQ-30, MEAQ-30 past week, CFQ-MI, CFQ-MI past week, PHLMS, PHQ-9, PCL-5, E-MIS, AUDIT, BAM-R and ASIQ). Participants and the study assessor will be blind to condition. At the conclusion of the assessment session, participants will be randomized to ACT-MI or PCT-MI. The study biostatistician will predetermine group assignment through block randomization to ACT-MI or PCT-MI (block size = 4); stratified to condition based on previous participation in an Evidence-Based Psychotherapy (EBP). We chose to stratify participants based on past EBP participation as we believe previous treatment engagement could significantly impact responsiveness to treatment and thus want to ensure that the groups are as evenly distributed as possible based on this variable. We felt this was more important to prioritize than stratifying for diagnosis given the transdiagnostic nature of the proposed intervention. Randomization results will be concealed in a sealed envelope until the end of the baseline assessment session. ***Treatment Participation.*** Participants randomized to either ACT-MI or PCT-MI will complete the intervention in an outpatient context. When necessary, ACT-MI and PCT-MI will be conducted over a VA approved videoconferencing platform. The treatments will be delivered across twelve group sessions. Investigators will attempt to offer treatment as quickly as possible, however, this will be dependent on group start dates. Participants will

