Aim 2: Determine the feasibility of the efficacy study design. Feasibility will be assessed by examining the following outcomes related to recruitment, retention, and provider adherence **a) Participant recruitment rates.** The number of participants approached for the study who are eligible to participate and of those, the number who enroll in the study (i.e., willingness to participate) will be evaluated. Feasibility will be defined as $\geq 50\%$ eligible and of these $\geq 30\%$ willing to participate in the proposed time frame. **b) Participant Retention.** Participant completion of ACT-MI will be measured by the percentage of participants who complete treatment and receive an adequate dose (completed a minimum of 70% of the intervention). Reasons for termination will be examined via the RT-C/T. The percentage of participants lost to follow up (LTFU) will be calculated as the percentage of participants who fail to complete one-month and three-month follow-up visits, with $\leq 30\%$ LTFU considered feasible. This will inform the necessary sample size and treatment retention strategies for future studies. **c) Provider adherence.** To examine the extent to which ACT-MI can be delivered as intended ($\leq 15\%$ of deviations for each clinician across participants on the treatment fidelity checklist), the proportion of sessions in which each clinician achieved acceptable fidelity out of all of the clinician’s sessions will be reported for all study clinicians. Qualitative review of fidelity checklists will be used if treatment fidelity is less than desired and areas of difficulty will be identified to inform training procedures for clinicians and treatment manual revisions.

Aim 3: Select measures and calculate necessary sample size for a future efficacy study. Evaluate candidate measures based on the following factors: (1) Amount of missing data and its distribution for all measures across groups; (2) means, standard deviations, and 95% confidence

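### Inclusion criterion 5 makes willingness to be randomised part of eligibility, so Aim 2a's eligible and willing rates depend on the stage at which a criterion-5 refusal is recorded

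*Combined protocol and SAP*

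**What the plan says.** Section I, Aim 2 (1) takes the "number of participants approached for the study who are eligible and of those, the number who enroll in the study (i.e., agree to participate"). Section VII, Aim 2 a) repeats this for those approached "who are eligible to participate and of those, the number who enroll in the study (i.e., willingness to participate) will be evaluated". Both places set the same bars: at least 50% of those approached eligible, and at least 30% of the eligible willing.

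Section IV.B, Inclusion Criteria, item 5 reads "Willing to be randomized and participate in either of the two conditions" and takes its information from self-report or the screening interview. The sentence that introduces the criteria is "All data will be collected from eligible and willing Veterans that meet the following eligibility criteria". The design paragraph of section IV.C speaks of Veterans "who are eligible and interested in participating in the study will be enrolled and randomized".

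Section IV.C, Procedures gives the order of events. Study details are shared first, then "potential participants will be given the option to provide verbal consent and complete a verbal screening interview based on inclusion and exclusion criteria". Willingness comes up again at the baseline session: "After demonstrating understanding of the postcard consent and indicating willingness to participate", participants go on to the safety measure and the assessments. Under Recruitment, Veterans reached by mail are screened only if they are still interested after hearing the details.

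For telehealth, section I (Aim 5) promises separate feasibility analyses for in-person and telehealth data. Section VII (Aim 4 and Aim 5) carries this out by repeating the Aim 2 analyses on Veterans who took part remotely.

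**The concern.** The two rates are meant to separate two obstacles: too few Veterans fit the entry criteria, or too few of those who fit agree to join. With criterion 5 inside eligibility, one kind of refusal can fall on either side. A Veteran who declines randomisation at the screening interview fails an inclusion criterion and leaves the eligible group. One who declines it at baseline is eligible but not enrolled. The second rate is then taken among Veterans who have already said that they accept randomisation.

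These two rates are the plan's definition of recruitment feasibility for the efficacy design. Read literally, they can show the 30% bar as met when fewer than 30% of otherwise eligible Veterans enrol. They can also show the 50% bar as missed when the entry criteria are not the obstacle. Nor does the plan say who counts as approached, or how Veterans who decline before screening are handled.

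Aim 5 has a related gap. Veterans who took part remotely have all been found eligible and enrolled, so that set cannot inform either recruitment rate. Inclusion criterion 6 adds a device and privacy requirement when groups run only by video, and its effect on recruitment would not show there.

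**Working it through.** **Inputs.** From the documents: 72 enrolled (section VII, Sample Size; 36 × 2 = 72 checks) and the bars of 50% and 30% (section VII, Aim 2 a). The bars are preset, so there is no calculated figure to reproduce. The documents give no number approached or eligible; those below are assumptions.

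**Notation.** A = approached; E = meets every criterion except number 5; r = criterion-5 refusals recorded at screening, at most E − 72.

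- As written: eligible rate = (E − r)/A; willing rate = 72/(E − r).
- Criterion 5 left out: E/A and 72/E, the same as r = 0.
- The product of the two rates is 72/A and does not depend on r.

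**Condition for meeting both bars as written.** 72/(E − r) ≥ 0.30 requires E − r ≤ 72/0.30 = 240. (E − r)/A ≥ 0.50 requires E − r ≥ 0.5A. So both are met when 0.5A ≤ E − r ≤ 240.

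| A (assumed) | E (assumed) | r | Eligible | Willing | Bars |
|---|---|---|---|---|---|
| 400 | 260 | 0 | 260/400 = 65.0% | 72/260 = 27.7% | second missed |
| 400 | 260 | 40 | 220/400 = 55.0% | 72/220 = 32.7% | both met |
| 400 | 260 | 100 | 160/400 = 40.0% | 72/160 = 45.0% | first missed |
| 400 | 220 | 0 | 220/400 = 55.0% | 72/220 = 32.7% | both met |
| 400 | 220 | 21 | 199/400 = 49.8% | 72/199 = 36.2% | first missed |
| 400 | 300 | 0 | 300/400 = 75.0% | 72/300 = 24.0% | second missed |
| 400 | 300 | 60 | 240/400 = 60.0% | 72/240 = 30.0% | both met |
| 300 | 200 | 0 | 200/300 = 66.7% | 72/200 = 36.0% | both met |
| 300 | 200 | 50 | 150/300 = 50.0% | 72/150 = 48.0% | both met |

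**Where the verdict moves.** With A = 400, both bars are met for r from 20 to 60 if E = 260, from 0 to 20 if E = 220, and from 60 to 100 if E = 300. Enrolled over approached is 72/400 = 18.0% in all of these.

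**Where it does not.** With A = 300 and E = 200, both bars are met for every r from 0 to 50. Above 480 approached, 0.5A exceeds 240, so the bars cannot both be met whatever the timing of refusals.

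**Telehealth set.** If n Veterans took part remotely, all n were eligible and all n enrolled. Both rates are n/n = 100% by construction.

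**The case against.** The best reply is that the team plainly treats eligibility and willingness as separate steps. Aim 2 puts one after the other, and both "All data will be collected from eligible and willing Veterans that meet the following eligibility criteria" and "who are eligible and interested in participating in the study will be enrolled and randomized" name them apart. That is probably the intent. But the first of these sentences introduces the very list that contains criterion 5, and nothing takes that criterion out of the eligibility count. The counting rule is still missing.

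It can also be said that details are shared before screening, so many refusals will come earlier. That is fair. However, the Moral Injury Interview at screening describes both treatments again, so criterion-5 refusals there remain possible, and the earlier ones have no stated place in either rate. A log of reasons could recover the split, but the two summary rates would not show it.

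For Aim 5, the word replicated could be taken to mean starting again from Veterans approached. The text, however, names remote participants as the source of the data.

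A reader might infer four stronger things that the documents do not support:

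- That any refusal moves between the rates. Only criterion-5 refusals do. A Veteran can accept randomisation and still decline at baseline, so the willing rate is not forced to 100%.
- That the verdict always turns on timing. It does so only for part of the assumed range.
- That confidence intervals could show whether the shift is real. The same Veterans are being classified in two ways; the difference is one of definition, not sampling.
- That a go/no-go decision is at risk. The analysis is descriptive, no action is attached to the recruitment rates, and neither the sample size nor any test is affected.

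**Conclusion.** The point holds as a defect in how Aim 2a is defined. As written, criterion-5 refusals at screening lower the eligible rate and raise the willing rate, and the willing rate is taken among Veterans who have already accepted randomisation. On assumed counts of 400 approached and 260 otherwise eligible, 40 such refusals turn a missed 30% bar (27.7%) into a met one (32.7%) with the same 72 enrolled. Other plausible counts leave the verdict unchanged. How often this would matter cannot be judged, because the documents give no numbers approached or eligible. The consequence is limited to interpreting a descriptive feasibility result, but that result is what Aim 2 sets out to deliver, and the correction is cheap. It should be fixed. The Aim 5 recruitment set, read as written, is uninformative and should be redefined at the same time.

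**What to change.** For Aim 2a only:

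- Determine eligibility on all criteria except number 5. Who may enter the trial does not change.
- Count criterion-5 refusals, and other non-enrolment among otherwise eligible Veterans, as not willing at whatever stage they occur. Exclusions first found at baseline, such as "Inability to demonstrate understanding of the postcard consent", still count as ineligible.
- Log the reason and stage of each non-enrolment.
- State who counts as approached, including whether an unanswered letter does.
- Report Veterans whose eligibility was never determined as a separate count. Do not screen further anyone who has refused.
- Report enrolled over approached alongside the two rates.

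For Aim 5, define the telehealth recruitment set by the modality on offer when the Veteran was approached, and the retention set by the modality planned for the assigned group at its start.

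The cost is a few sentences in section VII and one screening-log code. If Veterans have already been screened, the code must be assigned from whatever screening notes exist. The downside is that the reported willingness rate may be less favourable.

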intervals for all measures within and across groups; and (3) correlations and 95% confidence intervals between a self-reported clinically significant change measure and candidate measures across groups. Missing data and frequency distributions will be examined to identify measures that have the least amount of missing data, and the extent of outliers or other anomalies. Means and standard deviations will be examined to identify and exclude measures with limited sensitivity to change due to ceiling or floor effects, or restriction of range.⁷⁷ Finally, higher correlations between participants' scores on the Global Ratings of Change Scale and the candidate measures will suggest that these measures are more sensitive to clinically significant change. Confidence intervals will be examined to determine how much to emphasize these findings when selecting measures. The study team will work closely with [name] in considering these various statistics and their limitations when selecting the most promising outcome and mediational measures for the future efficacy study.

After the primary outcome measure has been selected, we will calculate the necessary sample size for the efficacy study. This will require an estimate of variability and effect size in the target sample. We will estimate variability across groups at baseline and the variability of change scores on the outcome measure. The estimate with the greatest variability will be used in our power calculation because it will provide the most conservative (i.e., largest) estimate of the necessary sample size. Unlike estimates of variability that can be based on the entire sample, estimates of effect sizes are limited by the group sizes. Increasingly, methodological experts argue against the use of pilot data to estimate effect sizes because of limitations related to sample size and protocol/intervention changes, leading to invalid estimates. Instead, best practice is to set the effect size in power calculations to whatever value is considered minimally clinically significant.¹⁷ We will use the available literature and consultation with experts on measures of functioning when selecting this effect size and calculating the necessary sample size for the efficacy study.⁶⁷

Aim 4 and Aim 5: The analyses described above for Aim 1 and Aim 2 will be replicated using data collected from Veterans who participated in the intervention and study remotely (i.e., using videoconferencing and REDCap).

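### Aim 3 reads correlation with a study-made change rating as sensitivity to clinical change, without checking that the rating reflects change rather than present state

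*Combined protocol and SAP*

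**What the plan says.** Section VII, Aim 3, judges candidate measures on three factors: the amount and pattern of missing data; means and SDs, used to screen out measures limited by ceiling, floor or narrow range; and "correlations and 95% confidence intervals between a self-reported clinically significant change measure and candidate measures across groups". The third is interpreted directly: a stronger association between "scores on the Global Ratings of Change Scale and the candidate measures will suggest that these measures are more sensitive to clinically significant change".

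Section IV.A, repeated in IV.C, describes the anchor. The GC "is a 6-item scale developed for the proposed study to assess self-report change following the interventions". Its sample item asks how the participant's present ability compares: better or worse "than my ability to live consistently with my values before I enrolled in the study". The support offered is one sentence: "The GC follows guidelines for an anchor-based approach to determining the minimally clinically important difference". No reliability or validity data are reported. The schedule is "Administration: Post-Treatment, One-month follow-up, Three-months follow-up".

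Two safeguards are stated. "Confidence intervals will be examined to determine how much to emphasize these findings when selecting measures", and the team will take advice "in considering these various statistics and their limitations when selecting the most promising outcome and mediational measures for the future efficacy study". The plan does not say whether a candidate enters the correlation as a follow-up score or a change score, or which GC visit is used. It plans no comparison of the GC with baseline scores.

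**The concern.** The GC asks for a judgement that depends on remembering an earlier state. At the three-month visit, that state lies before twelve sessions, three further months and any wait for a group to start. If sessions are weekly, as the alternation of process measures between odd and even weeks implies, this is about 12 + 13 = 25 weeks plus the wait. The GC is also completed in the same assessment as the candidate measures, so how the participant feels that day can colour both.

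If the rating mainly expresses present state, a high correlation with a candidate no longer means that the candidate picks up clinical change. The stake is the choice of measure: the one selected becomes the primary outcome of the efficacy trial and supplies the SD for its sample size. This study also compares original and past-week versions of the AAQ-II, MEAQ-30 and CFQ-MI. Such candidates may differ in stability, though the documents give no values.

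**Working it through.** **Inputs.** The documents give no figure for the GC correlations or for the stability of any measure. The only design number is enrolment: 36 × 2 = 72. Applying the plan's 30% loss threshold gives 72 × 0.70 = 50.4, so n = 50 and n = 72 are used below. All values of c, r, ρ and s are assumptions.

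**Notation.** B and F are a measure's baseline and follow-up scores, with equal SDs unless stated; r is their correlation; c is the GC–follow-up correlation. Measures are oriented so that higher is better.

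**1. Present-state anchor, change scores.** If the GC depends on F only:
- corr(GC, F − B) = c(1 − r)/√(2(1 − r)) = c√((1 − r)/2)
- c = 0.7, r = 0.3: 0.7 × 0.592 = 0.41
- c = 0.7, r = 0.8: 0.7 × 0.316 = 0.22

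Range over c, for r from 0.3 to 0.9: 0.24 down to 0.09 at c = 0.4; 0.36 to 0.13 at c = 0.6; 0.47 to 0.18 at c = 0.8.

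**2. Effect on ordering.** Two measures with c = 0.6 and r = 0.4 or 0.8 were compared in 20,000 simulated trials. With change scores, the less stable measure ranks higher in 77% of trials at n = 50 and 82% at n = 72. With follow-up scores the split is 50%: there is no tilt, but also no information on change. When the stable measure tracks present state better (0.7 v 0.5), the less stable one still ranks higher in 62–63%. For the same mean change of 0.5 SD, the standardized response mean is 0.5/√(2 × 0.2) = 0.79 for the stable measure and 0.5/√(2 × 0.6) = 0.46 for the other.

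**3. Instability from random error.** Let ρ be reliability, s true-score stability (r = ρs) and cT the GC correlation with the true follow-up score. Then corr(GC, F − B) = cT√ρ(1 − s)/√(2(1 − ρs)). With cT = 0.7 and s = 0.8:
- ρ = 1 (r = 0.80): 0.22
- ρ = 0.7 (r = 0.56): 0.12
- ρ = 0.375 (r = 0.30): 0.7 × 0.612 × 0.2/√1.4 = 0.07

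Error lowers the correlation. The tilt in steps 1 and 2 therefore concerns less stable true scores.

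**4. Unequal SDs.** If the follow-up SD is k times the baseline SD, the correlation is c(k − r)/√(k² + 1 − 2kr). At c = 0.6 and k = 1.2 it is 0.41 at r = 0.3 and 0.33 at r = 0.8, so the tilt shrinks. At k = 0.8 it is 0.28 and 0.00, so the tilt grows.

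**5. Can the planned data show which kind of anchor this is?**
- Present-state anchor: corr(GC, B) = cr, which is positive. At c = 0.7 it is 0.21 (r = 0.3) and 0.56 (r = 0.8). Given F, the baseline coefficient is proportional to cr − rc = 0. With measurement error it is proportional to cT√ρ·s(1 − ρ), which is above zero.
- True-change anchor correlating 0.6 with change: the correlations with F and B are equal and opposite, ±0.6√((1 − r)/2). This is ±0.33 at r = 0.4, ±0.27 at 0.6 and ±0.19 at 0.8. The regression coefficients are also equal and opposite.

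For r = 0.8 and c = 0.6, the positive baseline correlation (0.48) is significantly above zero in about 95% of trials at n = 50 and 99% at n = 72. The check is workable at this sample size.

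**The case against.** The plan is descriptive, and factor (3) is one input among three. Confidence intervals and limitations are to be weighed, and the wording is only that higher correlations suggest sensitivity. A reader might infer that measures are ranked mechanically on the GC; the documents do not support that. Sensitivity to change is also approached through the ceiling, floor and range screen and, for process measures, through repeated administration during treatment. The GC is said to follow published guidance and is also given at post-treatment, where recall is shorter. The tilt needs two conditions that are not established: a rating driven by present state, and the use of change scores.

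Most of this stands and limits the claim. It does not remove the gap. Confidence intervals describe sampling error: 0.33 at n = 50 has an interval of 0.06 to 0.56, centred on the same quantity whether or not the anchor measures change. The reference to limitations names no check. The other two factors do not relate a measure to change that participants themselves report. If follow-up scores are used, the tilt disappears, but under a present-state anchor the correlation then carries no information on change.

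**Conclusion.** The point holds as a gap in the plan. Factor (3) gives a clinical-change meaning to a correlation with a study-made recall rating, and nothing planned tests whether the rating reflects change. The size under a present-state anchor, 0.41 v 0.22, rests on assumed values: c = 0.7, r = 0.3 and 0.8, equal SDs, similar reliability and a similar link to present state. It also takes the extreme case of a rating with no information on change beyond present state.

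Two stronger readings are not supported. A reader might conclude that noisy or less reliable measures would be favoured; step 3 shows the reverse, since random error pulls the correlation down to 0.07. A reader might also conclude that the GC is known to be invalid. The documents report no validation, which is a different statement, and nothing in them shows that the GC follows present state. The case for acting is that the risk bears on the choice of primary outcome and can be examined almost without cost.

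**What to change.** Add to Aim 3: for each candidate measured at baseline, oriented so that higher is better, report the GC correlation with baseline, follow-up and change scores, each with a 95% CI, and the regression of GC on follow-up and baseline. Name the post-treatment GC, which has the shortest recall, as the main anchor.

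Judge the anchor from the pattern across all measures. For similar SDs, a change rating should relate to baseline with opposite sign and similar size to follow-up. If baseline relations are generally positive, or near zero given follow-up, give factor (3) little weight in selection. Do not apply a pass/fail test measure by measure: for a valid but modest anchor (0.3 with change, n = 50), the baseline coefficient would be significantly negative in only about 39–53% of simulated trials, so sound measures would often lose the criterion by chance.

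The cost is a few extra correlations and one regression per measure on data already planned. The downside is that factor (3) may carry less weight in the final choice.
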